Date: December 14th 2020

**Self-Assembled Modified Macintosh Video laryngoscope versus McGrath
MAC[®] Video laryngoscope: Which is Better?**

[name], [name], [name]
Department of Anesthesiology and Intensive Care
Faculty of Medicine, Universitas Indonesia–RSUPN dr. Cipto Mangunkusumo
[name]

Background

Endotracheal intubation, the gold standard in definitive airway management, is a procedure for inserting an endotracheal tube (ET tube) with the help of a laryngoscope. A study showed that 94% of intubation done by skilled operators would be successful in 1 to 2 attempts. In contrast, non-skilled operators had only 82% first-attempt success rate with 13.2% requiring 3 or more attempts, and 10.3% taking over 10 minutes.^{1,2} One of the biggest upgrades in the recent decade to improve this success rate is the addition of video camera to a laryngoscope, reintroducing the device as a Video laryngoscope (VL). McGrath MAC[®] laryngoscope is one of the most widely used commercial video laryngoscopes that utilize a modified Macintosh blade, with a video camera and a light source attached at the end of the blade. The image is displayed in the *liquid-crystal display* (LCD) monitor mounted on the handle of the blade.^{3,4}

VL has been shown to improve visualization of the larynx.^{5,6,7,8} However, several studies showed that intubation time with McGrath MAC[®] is the same or even longer compared to conventional macintosh blades.⁷⁻¹⁰ Insertion of ET tube through the vocal cords is also more difficult even though it is clearly visualized because the ET tube is in contact with the anterior tracheal wall, and therefore a stylet is needed to bend the tip of the ETT to an angle $> 35^\circ$.^{3,10,11} McGrath's blades are also less effective than the wider sized Macintosh blades to displace the tongue and expanding the area for visualization of the larynx and ET tube insertion¹⁰

Despite the advantages of video laryngoscope, the expensive price becomes a problem, especially in developing countries.^{6,12} As an alternative, we modified a classic Macintosh laryngoscope by attaching a flexible fiber optic-like camera to its blade. We compared the intubation time, success first attempt rate, laryngeal visualization, complications, and user satisfaction between this self-assembled video laryngoscope and McGrath MAC[®].

Research Methods

This is an experimental single-blinded randomized clinical trial conducted in the operating room for elective surgery at the dr. Cipto Mangunkusumo Hospital, a tertiary national referral hospital in Jakarta, Indonesia from June to August 2020. The sample size of 62 patients was calculated using numerical hypothesis testing formula for two unpaired populations with an

additional 10% of presumed sample dropout. Ethical clearance was obtained from Universitas Indonesia Ethical Board Committee.

All adult patients (18-65 years old), ASA I-II, with Body Mass Index (BMI) of 18 – 30 kg/m² scheduled for elective surgical procedures under general anaesthesia were included. All subjects provided written consent. We exclude patients with a difficult airway, pregnancy, cardiac condition, and neuromuscular disease.

The self-assembled modified Macintosh video laryngoscope (SAM-VL) used in this study was constructed from a portable video camera with a Wi-fi connection (Wi-fi Endoscope Video Camera model YPC99) attached to a no. 4 Macintosh Laryngoscope blade (Riester no.7040). The video signal is transmitted to an Android-based mobile phone (Android version 7.0). The portable 2 megapixels video camera is 8 mm in diameter with 8 LED lights for adjustable lighting level and 3 meters cable length. Video resolution output is 640x480 pixels (VGA) and 1280x720 pixels (HD). The camera has a 70° visual angle with a focal length of 4– 6cm and is water-resistant. The camera was taped to the Macintosh blade at a distance of 5 cm from the distal end of the blade, using transparent waterproof Leukofix[®] tape. After installation, the camera was oriented on a flat plane to set the desired image. The video images are then viewed on the mobile phone screen using the Y-camera app (downloadable for free in Google Play Store for Android). The total cost for this camera device assembly was Rp260.000 (roughly 20 USD), excluding the Android phone. After intubation, the camera is removed from the Macintosh blade and the camera tip that enters the patient's oral cavity is flushed with running water and washed with soap for at least two minutes, using a soft bristle brush to remove any soil if needed. After drying, the camera is wiped with a 70% alcohol swab before the next procedure.

Randomization was done with tables and then presented in a closed envelope when the patient arrived at the operating room to determine the intervention group: (1) the Self-Assembled Modified Macintosh Video laryngoscope (SAM-VL) group or (2) the McGrath MAC[®] video laryngoscope (McGrath) group. The laryngoscopist is the one who opened the envelope. A research assistant helped to prepare the laryngoscope according to the randomization results.

Anaesthesia monitoring was conducted following ASA standard and included ECG, non-invasive blood pressure, pulse oximeter, etCO₂, and temperature. Initial hemodynamic status

of the patient before induction including systolic, diastolic, mean arterial pressure, pulse, and peripheral oxygen saturation was noted.

Anaesthesia was co-induced intravenously with fentanyl 2 µg/kg, propofol 2 mg/kg, and rocuronium 0.6 mg/kg. Medications were titrated to effect. Subjects were given positive pressure mask ventilation with 80% oxygen for 3 minutes. Hemodynamic status was recorded three times: (1) pre-induction, (2) at 3 minutes after co-induction medications were given, and (3) after tracheal intubation in confirmed.

The intubation time “A” recording began when the tip of the laryngoscope blade passed through the incisors until the operator was able to achieve the best visualization of the glottis. The “B” intubation time recording began when the operator received visualization of the glottis and ended after the ET tube was confirmed to enter the trachea. Intubation time “B” consists of two components, insertion of the ETT into the vocal cords and connecting the breathing circuit so that the etCO₂ wave appeared on the monitor. When inserting the ET tubes, all operators were assisted with a stylet. To minimize the delay in connecting the circuit, one assistant was present to help the operator.

Intubation was done using ET tube No.7.5 for men and No.7 for women with the help of a stylet. Subjects underwent laryngoscopy and intubation with either McGrath MAC[®] video laryngoscope or SAM-VL according to randomization. During visualization of the glottis, the operator mentioned the POGO (Percentage of Glottic Opening) score visualized, with a scale ranging from 0–100%. Successful intubation was confirmed by capnography tracing. The SAM-VL can record both photo and video formats. McGrath MAC[®] screen can only be used for visualization, but the image cannot be recorded. Thus, a smartphone video camera is used to record images from the McGrath MAC[®] screen.

One attempt to intubate was noted if the ET tube was successfully placed into the trachea on the first attempt. If the laryngoscope blade was removed from the mouth and then reinserted, consequently the researcher noted the number of intubation attempts. If the intubation attempt was unsuccessful 3 times and/or the intubation time exceeds 120 seconds, the subject was dropped out.

If during the procedure an emergency or desaturation of $\leq 90\%$ occurred, it would be managed following ALS algorithms and the subject was dropped out from the study. Any complication throughout the procedure was noted. This study also includes a survey to evaluate the operator's subjective experience using three questionnaires in Likert scale format. The items evaluated are ease in blade insertion, device maneuverability, glottis visualization, and overall satisfaction rating.

The results were calculated using the *Statistical Package for Social Scientists* (SPSS) 24. Analysis of the duration of intubation (numerical data) was done with an unpaired *t-test* for data with normal distribution, and Mann-Whitney if the distribution was not normal. The results were considered significant if the p-value was < 0.05 .

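### The recording procedure differs by arm during the timed intubation: an added smartphone films the handle-mounted McGrath screen, while the SAM-VL can record in its own app

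*Combined protocol and SAP*

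**What the plan says.** Everything here is in the combined protocol and SAP, whose sections are unnumbered.

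- **Recording, SAM-VL arm (Research Methods, intubation procedure).** "The SAM-VL can record both photo and video formats".
- **Recording, McGrath arm (same paragraph).** "McGrath MAC[®] screen can only be used for visualization, but the image cannot be recorded"; as a consequence, "a smartphone video camera is used to record images from the McGrath MAC[®] screen".
- **Where each display sits.** Background describes the McGrath display as a "monitor mounted on the handle of the blade". For the SAM-VL, Research Methods says: "The video images are then viewed on the mobile phone screen using the Y-camera app".
- **What is timed (Research Methods, intubation times).** Time A "began when the tip of the laryngoscope blade passed through the incisors until the operator was able to achieve the best visualization of the glottis". Time B "began when the operator received visualization of the glottis and ended after the ET tube was confirmed to enter the trachea", and it includes connecting the circuit until the capnography wave appears.
- **Staff during intubation.** "To minimize the delay in connecting the circuit, one assistant was present to help the operator". A research assistant also prepares the allocated laryngoscope. Nobody is named as doing the filming.

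The document does not state whether the phone is hand-held or fixed, where it is placed, when filming starts and stops, whether every case was recorded in either arm, or whether any outcome was read from the recordings.

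**The concern.** The trial compares two devices on intubation time, so anything done around the operator during that time should be the same in both arms unless it belongs to the device. Pointing a second camera at the McGrath screen is not part of using a McGrath. It is done for the study, and it is described for one arm only.

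The McGrath screen moves with the operator's hand, and the camera needs a line of sight to the display the operator is watching. If that leads to crowding, glare, a pause or a change of grip, McGrath times lengthen and SAM-VL times do not. If the circuit assistant is the one filming, time B is exposed directly. Randomisation does not remove an effect that is tied to allocation, and neither the t-test nor the Mann-Whitney test can separate it from a device effect. The operator's ratings of maneuverability, visualization and satisfaction could be affected in the same way. Any such effect would favour the device that the investigators assembled.

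**Working it through.** **Step 1. Does recording differ by arm?** Yes, in method. The McGrath sentence gives the device's inability to record as the reason for external filming, and no external filming is described for the SAM-VL. A phone is also present in the SAM-VL arm, as its display. The difference is therefore the additional camera aimed at the McGrath screen, not the mere presence of a phone.

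**Step 2. Does filming overlap the timed interval?** At least in part. The McGrath shows a laryngeal image only while the blade is in the mouth. Time A begins at blade entry and time B runs on to confirmed placement, so filming that image falls inside A and the earlier part of B. The last part of B, connecting the circuit and waiting for the capnography wave, does not need the laryngeal view, so full overlap is not established. The overlap is an inference; the document does not state it.

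**Step 3. Is there anything that equalises it?** Nothing is described. The plan provides an assistant to limit delay at circuit connection, but has no corresponding provision for filming.

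**Step 4. What would a delay do?** The document gives neither a delay nor an SD, so this step illustrates sensitivity and estimates nothing.

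Inputs:
- Total sample 62 (Research Methods). Allocation is assumed 1:1, giving 62 / 2 = 31 per arm with no dropout.
- Significance level 0.05 (Research Methods), assumed two-sided.
- SD 10 or 15 s: assumed.
- Mean delay in the McGrath arm 0, 1, 2 or 5 s: assumed.
- No true difference between devices.

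Formulas: SE = SD × √(2/31), with 31 + 31 − 2 = 60 degrees of freedom and a critical value of 2.00. The noncentrality is delay / SE, and the rejection probability is the two-sided tail of the noncentral t.

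- SD 10 s: SE = 10 × √(2/31) = 2.54 s
- SD 15 s: SE = 15 × √(2/31) = 3.81 s

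| Mean delay, McGrath arm | Delay / SE (SD 10 s) | False-positive rate (SD 10 s) | Delay / SE (SD 15 s) | False-positive rate (SD 15 s) |
|---|---|---|---|---|
| 0 s | 0 | 5% | 0 | 5% |
| 1 s | 0.39 | 6.7% | 0.26 | 5.8% |
| 2 s | 0.79 | 12.1% | 0.52 | 8.1% |
| 5 s | 1.97 | 49% | 1.31 | 25% |

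With 28 per arm, an assumed figure if about 10% drop out, the rates are slightly lower: 7.8-11.4% at 2 s and 23.2-45.1% at 5 s.

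The table shows what a shift of a given size in one arm does to the test. It does not show that filming causes such a shift.

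**The case against.** The strongest reply is that no harm is shown. The plan says only that a smartphone is used. A fixed camera, or a third person standing clear, might have no effect, and a delay of zero fits the text as well as any other value. This stands. The point is an unequal and under-described procedure, not a demonstrated bias.

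A reader might infer three stronger things that the document does not support:

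- **That the SAM-VL records every case by itself and nobody films in that arm.** The text says only that the device can record. What was done, and in which cases, is not stated for either arm.
- **That results are biased against the McGrath, or that the error rate really reaches 49%.** The direction holds only if there is a delay. The upper figure needs an average of 5 s added across the whole McGrath arm with an SD of 10 s, and nothing in the document supports either number.
- **That filming could simply be dropped because no outcome uses it.** The POGO score is spoken by the operator and success is confirmed by capnography, but the document does not say whether recordings were used to check anything. The operator opens the allocation envelope, so images may be the only check on a score called out by someone who knows the arm.

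It can also be said that the remedy comes late: the document is dated December 2020 and gives June to August 2020 as the conduct period. That bears on which action is still open, and the fix allows for it.

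**Conclusion.** The concern holds as a possible performance bias of unknown size. The text establishes that external filming is described for the McGrath only, that it is a study procedure and not part of using the device, and that nothing in the plan makes it equal between arms. That it overlaps at least part of the timed interval is a firm inference. The text does not establish that filming slows or distracts anyone.

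If there is an effect, it falls on McGrath times and operator ratings alone and favours SAM-VL. On the assumptions above, a 1 s mean delay would barely matter, 2 s would roughly double the false-positive rate (8-12% against 5%), and 5 s would make the comparison unreliable (25-49%). The point is worth correcting because the remedy is cheap, not because a distortion has been shown.

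**What to change.** Record both arms in the same way. Use the same external smartphone, in a fixed position outside the operator's line of sight, aimed at the McGrath screen in one arm and at the SAM-VL phone screen in the other. State that neither the operator nor the circuit assistant handles it, and that the SAM-VL in-app recorder does not replace it. Keep the filming, since it may be the only image check on the POGO score.

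The cost is a sentence or two in Research Methods, using a smartphone the trial already has. The downside is the same small filming burden in the SAM-VL arm.

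If data collection is already complete, the procedure cannot be changed. In that case report who filmed, from where and in which cases for each arm, say whether filming was hands-off for the operator and the circuit assistant, and list the difference between arms as a limitation of the intubation-time and operator-rating comparisons.

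### Randomised patients are dropped for failed, slow or complicated intubation, and no rule keeps them in the analysis

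*Combined protocol and SAP*

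**What the plan says.** The Background lists the outcomes: "We compared the intubation time, success first attempt rate, laryngeal visualization, complications, and user satisfaction". Under Research Methods, allocation is "presented in a closed envelope when the patient arrived at the operating room to determine the intervention group", so it precedes laryngoscopy.

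Two later sentences in Research Methods remove patients:

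- On attempts and time: "If the intubation attempt was unsuccessful 3 times and/or the intubation time exceeds 120 seconds, the subject was dropped out".
- On an emergency or desaturation to 90% or below: "it would be managed following ALS algorithms and the subject was dropped out from the study".

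Four other statements bear on the point:

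- Intubation time B "ended after the ET tube was confirmed to enter the trachea".
- The sample size of 62 includes an "additional 10% of presumed sample dropout".
- On repeat attempts: "If the laryngoscope blade was removed from the mouth and then reinserted, consequently the researcher noted the number of intubation attempts".
- On harms: "Any complication throughout the procedure was noted".

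The closing analysis paragraph names a t-test or Mann-Whitney test for duration and a significance level. It defines no analysis population, censoring rule, score for failures, replacement rule or sensitivity analysis.

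**The concern.** All the triggers occur after allocation, and each is an extreme value of something the trial compares. Randomisation does not protect a comparison from which patients are removed according to their result, because the removals can differ by device.

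- **Intubation time.** The upper tail is cut off. The device that fails or runs long more often looks better than it is.
- **First-attempt success.** The effect is partial and can go either way. A patient intubated on the second or third attempt within 120 s stays in as a first-attempt failure. A three-attempt failure leaves the denominator, which raises the rate. A slow first-pass success removed by the 120 s trigger lowers it.
- **Complications.** Desaturation and emergencies are among the events one would compare, and they are themselves grounds for removal.

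The title asks which device is better, so the rule bears on the main question.

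**Working it through.** **Is exclusion the right reading?** The emergency sentence removes the patient from the study, and the sample size is enlarged for dropout. That enlargement is needed only if dropouts do not contribute data. The full sample size cannot be rebuilt, because effect size, SD and power are not given. The last step fits 28 evaluable per arm: 28 × 1.10 = 30.8, rounded up to 31, and 2 × 31 = 62. If the sponsor did intend to keep these patients, a rule is still missing: time B ends only at confirmed tube placement, so a patient never intubated has no value to analyse.

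**Assumptions for the illustrations.** 1:1 allocation (31 per arm), log-normal times, and a two-sided Mann-Whitney test at 0.05. The documents give no times, SDs or failure rates by device, so every medians, spreads and failure figure below is assumed.

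**1. Deleting failures.** Both arms have median 40 s and log-SD 0.4, so the mean is 40 × exp(0.4²/2) = 43.3 s. One arm has 2% failures. With failures kept and set to 120 s for the mean, the expected difference is (p − 0.02) × (120 − 43.3). Rejection rates come from 20,000 simulated trials per row, with kept failures given the worst rank.

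| Failures, other arm vs 2% | Mean difference, kept | Rejection, kept | Mean difference, deleted | Rejection, deleted |
|---|---|---|---|---|
| 5% | 0.03 × 76.7 = 2.3 s | 5.3% | about 0 s | 4.8% |
| 10% | 0.08 × 76.7 = 6.1 s | 8.0% | about 0 s | 4.9% |
| 20% | 0.18 × 76.7 = 13.8 s | 22.4% | about 0 s | 5.1% |

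**2. Deleting times over 120 s.** With median m, log-SD s and z = (ln 120 − ln m)/s, the full mean is m·exp(s²/2). The mean after truncation is that value times Φ(z − s)/Φ(z).

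| Medians | Log-SD | Full difference | After deletion | Shrinkage |
|---|---|---|---|---|
| 50 vs 40 s | 0.4 | 10.8 s | 9.9 s | 9% |
| 60 vs 45 s | 0.4 | 16.2 s | 13.5 s | 17% |
| 70 vs 50 s | 0.4 | 21.7 s | 16.0 s | 26% |
| 50 vs 40 s | 0.5 | 11.3 s | 8.9 s | 22% |
| 60 vs 45 s | 0.5 | 17.0 s | 11.7 s | 31% |
| 70 vs 50 s | 0.5 | 22.7 s | 13.5 s | 40% |

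The share of patients over 120 s runs from 1.4% vs 0.3% (first row) to 14.1% vs 4.0% (last row).

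**3. First-attempt success.** Take an arm of 31 with 6 first-attempt failures: 25/31 = 80.6%.

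- Removing 1, 2 or 3 three-attempt failures gives 25/30 = 83.3%, 25/29 = 86.2% or 25/28 = 89.3%.
- Removing 1, 2 or 3 slow first-attempt successes gives 24/30 = 80.0%, 23/29 = 79.3% or 22/28 = 78.6%.

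**The case against.** Four points deserve weight.

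- **Exclusion is inferred.** The attempts-and-time sentence says only that the subject was dropped; the words about leaving the study appear in the emergency sentence. This stands as a caveat. It does not rescue the plan, because a scoring rule is missing on either reading.
- **Complications were recorded.** The sentence after the desaturation rule says so. Loss of these events is therefore possible, not shown. What is missing is any statement that dropped patients enter the comparison between arms.
- **Failures may be rare.** The Background cites 94% success within two attempts for skilled operators, and 13.2% of non-skilled operators' cases needing three or more. If those rates carry over, three-attempt failure is at most about 6% or 13.2%, and patients with a difficult airway are excluded. The 20% scenario then lies outside the documents' own figures, and at 5% the effect is small. However, operator skill is not stated, these rates are not specific to either device, and they do not bound the 120 s trigger.
- **Shrinkage of means overstates the effect on the planned test.** Skewed times would go to Mann-Whitney. For the six truncation scenarios, in table order, power with long times kept as worst rank versus deleted is 56% vs 53%, 76% vs 71%, 89% vs 82%, 38% vs 35%, 58% vs 48% and 71% vs 55%. The loss is modest at log-SD 0.4 and substantial only with wide spread and a large difference. It appears in every scenario.

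**Conclusion.** The concern holds and must be fixed. Followed as written, the plan removes randomised patients because of their results on the outcomes it compares, and it gives no rule for analysing them. This rests on the design, not on a demonstrated size: the actual bias is unknown and could be small if few patients were dropped. Under the assumed distributions it ranges from negligible (5% vs 2% failures) to the loss of a 13.8 s difference, with a 9% to 40% shrinkage of a true mean difference from the 120 s limit alone. In an arm of 31, one removed three-attempt failure moves first-attempt success from 80.6% to 83.3%. A larger sample does not correct this.

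**What to change.** Leave the clinical limits as they are and change only the analysis.

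1. In both dropout sentences, state that the patient's study participation ends but the patient is analysed in the randomised group.
2. Score first-attempt success by what happened on the first attempt. A three-attempt failure counts as a first-attempt failure; a tube placed on the first pass after 120 s does not.
3. For time, give every patient not intubated within the limits, including any not intubated because of an emergency or desaturation, the shared worst rank in a Mann-Whitney test. Alternatively, censor the time at 120 s and name a method that handles censoring, since the planned tests do not.
4. State whether 120 s refers to time A, time B or their sum, and whether it is per attempt or cumulative.
5. Keep desaturation and emergency events in the complication comparison.
6. Report failures and dropouts by arm and reason.

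The document is dated December 2020 and describes conduct in June to August 2020. If the data are already collected, apply this as a reanalysis of all randomised patients. Attempts and complications were noted, but the text does not say that times were kept for dropped patients. Where they were not, say so and give best-case and worst-case results.

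The cost is two reworded sentences, one scoring rule and possibly a reanalysis. A rank or censored-time summary replaces a simple mean. The shared worst rank also discards any known time beyond 120 s and counts against the device some emergencies that it may not have caused; that is a choice to state openly.

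### Patients removed after randomisation for an emergency or desaturation should stay in their assigned arm for analysis, and the complication denominator should be stated

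*Combined protocol and SAP*

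**What the plan says.** All of this is in the combined protocol and SAP, whose sections are unnumbered.

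- **Allocation** (Research Methods, randomisation): the assignment is "presented in a closed envelope when the patient arrived at the operating room", and the laryngoscopist opens it. Induction follows, then mask ventilation ("Subjects were given positive pressure mask ventilation with 80% oxygen for 3 minutes"), then laryngoscopy.
- **Removal rule** (Research Methods, emergencies and desaturation): if an emergency occurs, or saturation falls to 90% or below, "it would be managed following ALS algorithms and the subject was dropped out from the study".
- **Complications** (the next sentence): "Any complication throughout the procedure was noted".
- **Outcomes** (end of Background): "We compared the intubation time, success first attempt rate, laryngeal visualization, complications, and user satisfaction" between the two devices.
- **Times** (Research Methods): time A runs from the blade passing the incisors to the best glottic view. Time B runs from that view to confirmed placement in the trachea.
- **Analysis** (last paragraph): a test is named only for duration of intubation, namely an unpaired t-test, "and Mann-Whitney if the distribution was not normal".

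The document defines no analysis set. It gives no rule for the data of removed patients, no denominator for complications and no reporting of removals by arm. A separate rule removes patients after three failed attempts or more than 120 seconds. It matters here only where one patient meets both rules.

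**The concern.** The removal happens after allocation and is triggered by something the allocated device may influence. A slow or repeated laryngoscopy is an obvious route to desaturation, and ease of laryngoscopy is what the trial compares. If the two devices lead to such events at different rates, or in different kinds of patient, those left in each arm are no longer the groups that randomisation formed. Times, first-attempt success, glottic view and satisfaction would then describe only patients who had no such event.

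The trigger also belongs to one of the compared outcomes. A reader of a reported complication rate cannot tell whether the removed patients are in the numerator, the denominator, both or neither.

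**Working it through.** **1. The plan's own figure.** The document gives 62 patients including 10% for dropout, but no effect size, standard deviation or power, so the full calculation cannot be rebuilt. Only the dropout step can be checked. If the number before inflation was 56 (inferred, not stated), then 56 × 1.10 = 61.6, rounded up to 62. That would allow for 62 − 56 = 6 losses. This fits a plan in which removed patients are not analysed, but it does not prove it. The figure of 62 is not in dispute.

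**2. Order of events.** Envelope, induction, mask ventilation, time A, time B. The document does not say where the procedure begins for the purpose of the removal rule, so an event during mask ventilation could also trigger it. In every case the removal follows randomisation. Only events from blade insertion onward can be due to use of the device.

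**3. How many patients.** The documents give no event risk, so r is assumed. Expected events = 62r; chance of no event = (1 − r)^62.

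| Assumed risk r | Expected events | Chance of none |
|---|---|---|
| 1% | 0.62 | 0.536 |
| 2% | 1.24 | 0.286 |
| 5% | 3.1 | 0.042 |

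**4. Complication rate.** The arm sizes are not stated; 31 per arm is assumed here and below. One event is 1/31 = 3.2 percentage points of that arm's rate.

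**5. First-attempt success.** For illustration, assume 26/31 = 83.9% in one arm with everyone kept.

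| Removed from the arm | Rate among those left | Change (points) |
|---|---|---|
| 1, first attempt failed | 26/30 = 86.7% | +2.8 |
| 1, first attempt succeeded | 25/30 = 83.3% | −0.5 |
| 3, all failed | 26/28 = 92.9% | +9.0 |
| 3, all succeeded | 23/28 = 82.1% | −1.7 |

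The sign depends on what happened to the removed patients, so no direction can be assumed.

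**6. Time.** Suppose completed times are alike in both arms, and k patients in one arm only have an uncompleted intubation that is ranked worst. The probability that a patient in that arm is slower than one in the other is 0.5 × (31 − k)/31 + k/31. For k = 1 this is 0.516; for k = 3 it is 0.548. Removing those patients gives 0.500, so each removal hides about 1.6 points.

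For scale, the standard error of this probability under no difference is √(63/(12 × 31 × 31)) = 0.074. One removal is therefore 0.016/0.074 ≈ 0.2 standard errors, and three in one arm are 0.048/0.074 ≈ 0.65.

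**The case against.** **The effect may be trivial.** The trial selects ASA I–II elective patients with a BMI of 18 to 30, and "We exclude patients with a difficult airway, pregnancy, cardiac condition, and neuromuscular disease". At a 1% or 2% risk, about one patient or fewer is affected. The larger shifts in the working need three events in one arm and none in the other. If events were unrelated to device, three events would all fall in one arm with probability 2 × (31 × 30 × 29)/(62 × 61 × 60) = 0.24. The 26/31 baseline is also an assumption. All of this stands, and it limits the size that can be claimed. It does not make the rule sound: whether the effect was nil can be known only if the removals are reported by arm.

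**Complications are covered.** A reader might infer that the removed patients' complications vanish. The documents do not support that. The sentence directly after the rule says complications were noted, with no exception, and Background says they were compared. What is missing is the denominator and a statement that removed patients are included.

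**Exclusion is only inferred.** No sentence says that the times and attempts of removed patients are left out. That is the plain meaning of the rule, however, and nothing in the document restores them.

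**Keeping everyone could charge the device unfairly.** An event during mask ventilation is not a failed laryngoscopy, and a time A that was reached is valid even if intubation was then abandoned. Both points are right, and the fix respects them.

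**Conclusion.** The point holds and should be fixed. The plan states a rule that removes randomised patients because of an event the device may influence and that is itself a compared outcome. The time, first-attempt, glottic-view and satisfaction comparisons are therefore not protected by randomisation. For complications, the fault is limited to an unstated denominator and unstated inclusion.

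The size is unknown and may be zero. The number affected rests on assumed risks, and the per-event figures on an assumed 31 per arm. A reader might also infer that the rule flatters one device or inflates success rates. The documents give no event counts by arm, and removing a patient whose first attempt succeeded lowers that arm's rate, so neither inference is supported.

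**What to change.** Leave emergency management as it is, and separate stopping the study procedure from removal from the analysis. State that:

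1. Patients with an emergency or desaturation stay in their assigned arm. Each event counts as a complication of that arm, with all randomised patients as the denominator.
2. Every recorded outcome is used: time A if the glottic view was obtained, time B and attempt number if intubation was completed, and the POGO score and operator ratings if given.
3. If laryngoscopy with the allocated device began but intubation was not completed, the patient is a first-attempt failure. The worst rank in the Mann-Whitney test is given only for the time component not reached.
4. Events before blade insertion are reported by arm as complications. They are not scored as device failures in the main time and first-attempt analyses. A sensitivity analysis does score them, since the laryngoscopist may already know the allocation.
5. For a patient who also met the three-attempt or 120-second rule, this retention for analysis takes precedence.
6. Affected patients are listed by arm and reason, including a statement if there were none.

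The document is dated December 2020 and the study ran from June to August 2020, so this is a re-analysis of existing records. The scheduled readings ("Hemodynamic status was recorded three times: (1) pre-induction, (2) at 3 minutes after co-induction medications were given", and a third after confirmed intubation) include none during laryngoscopy, so some event details may be hard to recover. Say where records are incomplete.

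The cost is a little more analysis work, a rank test in place of the t-test if any intubation was uncompleted, and possibly less favourable reported rates. No extra patients or procedures are needed.
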